### **Partial Response**

Partial Response	PET-Based Response – PMR	CT/MRI-Based Response – PR
Target lesions	Score 4 or 5 without new lesions Reduced overall uptake (extent and/or intensity) compared with baseline	≥50% decrease from baseline in SPD of target lymph nodes and extranodal sites (up to 6)
Non-target lesions	Not applicable	Anything other than progression
Organ enlargement	Not applicable	Spleen must have regressed by ≥50% in excess length
New lesions	None	None
Bone marrow	Residual uptake higher than uptake in normal marrow but reduced compared with baseline.  If there are persistent focal changes in the marrow in the context of a nodal response and without recent growth factor use, perform biopsy, or consider MRI, or an interval scan.	Not applicable
Abbreviations: CT=computed tomography; MRI=magnetic resonance imaging; PET=positron emission tomography; PMR=partial metabolic response; PR=partial response; SPD=sum of products of diameters.		

### **Stable Disease**

Stable disease	PET-Based Response – SMD	CT/MRI-Based Response – SD
Target lesions	Score 4 or 5 (without new lesions)  No significant change in FDG uptake from baseline or nadir	<50% decrease from baseline in SPD of target lesions.  No lesion shows progression
Non-target lesions	Not applicable	No increase consistent with progression
Organ enlargement	Not applicable	No increase consistent with progression
New lesions	None	None
Bone marrow	No change from baseline	Not applicable
Abbreviations: CT=computed tomography; FDG=2 fluorodeoxyglucose; MRI=magnetic resonance imaging; PET=positron emission tomography; SD=stable disease; SMD=stable metabolic disease; SPD=sum of products of diameters.		

### **Progressive Disease**

Progressive disease	PET-Based Response – PMD	CT/MRI-Based Response – PD
Target lesions	Score 4 or 5 with an increase in overall uptake (extent and/or intensity) compared within nadir	Growth of any target lesion: Increase $\geq 50\%$ from nadir PPD and Increase in LD i or SD i from nadir of: $\geq 0.5$ cm for lesions $< 2$ cm $\geq 1.0$ cm for lesions $\geq 2$ cm and Current LD i $> 1.5$ cm for a lymph node or $\geq 1.0$ cm for an extranodal lesion
Non-target lesions	Not applicable	Clear progression of pre-existing non-target lesions
New lesions	New FDG-avid foci consistent with lymphoma rather than another cause (eg, infection, inflammation). If uncertain regarding cause of new lesions, biopsy or interval scan may be considered.	Regrowth of previously resolved lesions A new node $> 1.5$ cm in LD i A new extranodal site of any size so long as its presence is unequivocal and attributable to lymphoma
Organ enlargement	Not applicable	When splenomegaly was already present, the excess length must increase by $\geq 50\%$ ( $\geq 1$ cm absolute increase) from nadir. If no prior splenomegaly, or prior splenomegaly had resolved, spleen length must increase by $\geq 2$ cm to $> 13$ cm.
Bone marrow	New or recurrent FDG-avid foci, confirmed by biopsy	New or recurrent involvement
Abbreviations: CT=computed tomography; FDG=2 fluorodeoxyglucose; LD i =longest diameter; MRI=magnetic resonance imaging; PET=positron emission tomography; PD=progressive disease; PMD=progressive metabolic disease; PPD=product of perpendicular diameters; SD i =short axis diameter.		

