### **Anatomic Response**

The anatomic response should be assessed at each post-baseline timepoint based on the criteria below. Liver size alone should never be the basis for response determination by itself, but only support the assessment as supplemental information.

Target	Non-Target	Spleen	New Lesions	Anatomic Response
CR	CR	CR	No	CR a
CR	CR	PR	No	PR b
CR	SD	CR	No	PR b
PR	CR/SD	CR/PR	No	PR
PR	CR/SD	SD	No	SD
SD	CR/SD	CR/PR	No	SD
SD	CR/SD	CR/PR/SD	No	SD
Any non-PD	NE	CR/PR/SD	No	NE
NE	Any non-PD	CR/PR/SD	No	NE
PD	Any	Any	Any	PD
Any	PD	Any	Any	PD
Any	Any	PD	Any	PD
Any	Any	Any	Yes	PD
Abbreviations: CR=complete response; NE=not evaluable; PD=progressive disease; PR=partial response; SD=stable disease. a If the liver shows lymphoma involvement, it must resolve to allow CR. b Spleen can drive PR on its own if no target lesions were identified at baseline.				

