#### Metabolic response determination

Metabolic response categories are defined as follows:

Metabolic Response	Definition
Complete metabolic response (CMR)	A score of 1, 2, or 3.
Partial metabolic response (PMR)	A score of 4 or 5 (without new lesions), AND Overall uptake decreased compared with baseline
Stable metabolic disease (SMD)	A score of 4 or 5 (without new lesions), AND Overall uptake unchanged compared with baseline and nadir
Progressive metabolic disease (PMD)	A score of 4 or 5 with overall uptake increased compared with nadir, OR with new FDG-positive lesions consistent with lymphoma

In Waldeyer's ring or extranodal sites with high physiologic uptake or with activation within spleen or marrow (eg, with chemotherapy or myeloid colony-stimulating factors), uptake may be greater than normal mediastinum and/or liver. In this circumstance, CMR may be inferred if uptake at sites of initial involvement is no greater than surrounding normal tissue, even if the tissue has high physiologic uptake.

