#### Clinical Data

##### Bone marrow assessment

To allow an overall response of CR, the bone marrow must be clear of lymphoma (negative for lymphoma).

Lugano allows assessment of bone marrow based on FDG-PET if the lymphoma type is FDG-avid. Bone marrow on FDG-PET may be normal, may show diffuse uptake (clinical judgment is required, because this is also compatible with reactive changes due to chemotherapy or colony-stimulating factors), or may show focal increased uptake that is strongly indicative of lymphoma.

Note: In this protocol, if there is bone marrow involvement, bone marrow is required to confirm CR, regardless of FDG-avidity.

A negative PET allows the bone marrow to be declared negative, even without biopsy, and would support a CR overall (diffuse uptake compatible with reactive changes from chemotherapy or growth factor use can fall into this category). A PR may occur with residual uptake higher than uptake in normal marrow but reduced compared with baseline. If there are persistent focal changes in the marrow in the context of a nodal response, consideration should be given to further evaluation with MRI or biopsy or an interval scan.

Bone marrow aspirate or biopsy is required only as clinically indicated, or if FDG-PET evaluation of bone marrow is judged inconclusive. For lymphoma that is shown at baseline to be non FDG-avid, both aspiration and biopsy are required to declare marrow to be negative. If bone marrow biopsy is performed and shows lymphoma, the bone marrow is considered positive, regardless of the results of the PET.

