### **10.9.2.5 Overall Response**

Overall response at each timepoint is determined by combining the anatomic response, metabolic response, and clinical data. When both CT and FDG-PET are available, the overall response is driven primarily by the metabolic response. When only one imaging modality is available at a given timepoint, that modality is the main determinant of overall response.

Metabolic Response	Anatomic Response	Bone Marrow	Physical Examination	Overall Response
CMR	CR, PR, or SD	Negative	No lesions	CR
PMR	CR, PR, or SD	Any	No new lesions	PR
SMD	CR, PR, or SD	Any	No new lesions	SD
PMD	Any	Any	Any	PD
Any	PD	Any	Any	PD
Abbreviations: CMR=complete metabolic response; CR=complete response; PD=progressive disease; PMD=progressive metabolic disease; PMR=partial metabolic response; PR=partial response; SD=stable disease; SMD=stable metabolic disease.				

During determination of overall response, if no FDG-PET was performed at the timepoint in question, the results of a preceding PET may be “carried forward”, unless there has been worsening of disease on the CT. For example, if a post-baseline assessment shows a CMR on the PET, and PR on the CT, the overall response is CR. If the next timepoint shows continued PR on the CT, but there is no PET available, the overall response for that visit is still CR.

Lugano Classification 2014 [Cheson, B. D., et al 2014]

Barrington, SF et al 2014 [Barrington, S. F., et al 2014]

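### In the Lugano rules, new or recurrent marrow involvement proven only by biopsy is progressive disease in the summary table but PR, SD or unclassified in the overall-response table

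*Combined protocol and SAP*

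**What the plan says.** Participants other than those with CLL/SLL or WM/LPL are assessed by the Lugano rules in Section 10.9.2.

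- **Progressive Disease summary (10.9.2.2).** The marrow row has two cells. The PET-based cell, under PMD, reads "New or recurrent FDG-avid foci, confirmed by biopsy". The CT/MRI-based cell, under PD, reads "New or recurrent involvement" and carries no PET condition.
- **Anatomic Response (10.9.2.3.2).** The text says "The anatomic response should be assessed at each post-baseline timepoint based on the criteria below", and the table's columns are "Target Non-Target Spleen New Lesions Anatomic Response". Marrow is not among them.
- **Metabolic response determination (10.9.2.4).** PMD arises from increased uptake "OR with new FDG-positive lesions consistent with lymphoma". Partial metabolic response (PMR) and stable metabolic disease (SMD) are available only when there are no new lesions.
- **Bone marrow assessment (10.9.2.4).** "If bone marrow biopsy is performed and shows lymphoma, the bone marrow is considered positive, regardless of the results of the PET". The only consequence stated for a positive marrow is that CR is not allowed.
- **Overall Response (10.9.2.5).** "Overall response at each timepoint is determined by combining the anatomic response, metabolic response, and clinical data". In the table that follows, the partial-response row reads "PMR CR, PR, or SD Any No new lesions PR", so the marrow entry is *Any*. The SMD row has the same marrow entry. Complete metabolic response (CMR) appears only with a negative marrow. The two rows ending in PD are triggered by PMD and by anatomic PD.

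**The concern.** Section 10.9.2.2 refers the reader to the later sections for implementation, but those sections drop one of its own progression criteria. Two investigators could read the same visit differently and both be following the protocol: one records PD from the summary, the other PR or SD from the overall-response table.

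ORR and DOR are secondary endpoints and PFS is exploratory. A missed PD lengthens DOR and PFS. If the discrepancy falls at the visit that would give the first PR, it also adds a responder. In a study of about 6 to 12 participants across all diseases, one participant visibly moves the rate.

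The other two criteria sets in the same appendix do carry marrow through to PD in their overall-response rules: iwCLL in 10.9.1.3 and IWWM in 10.9.3.3. The Lugano omission therefore looks like an oversight.

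**Working it through.** The documents give no figure on this point, so the check traces the rules.

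**1. Overall-response table.** There are 4 metabolic categories (CMR, PMR, SMD, PMD) and 4 anatomic categories (CR, PR, SD, PD), so 4 × 4 = 16 combinations. Take the marrow as newly positive on biopsy and the physical examination as showing no lesions. The table in 10.9.2.5 returns:

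| Metabolic | Anatomic CR, PR or SD | Anatomic PD |
|---|---|---|
| CMR | no row (3) | PD (1) |
| PMR | PR (3) | PD (1) |
| SMD | SD (3) | PD (1) |
| PMD | PD (3) | PD (1) |

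The totals are PD 3 + 4 = 7, PR 3, SD 3 and no row 3. The 3 + 3 + 3 = 9 combinations without PMD or anatomic PD do not return the PD that the summary's CT/MRI cell prescribes. With a negative marrow, the PMR and SMD rows give the same answers, so in those rows the marrow result has no influence.

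**2. The two marrow cells traced separately.**
- *PET cell.* Biopsy-confirmed new FDG-avid foci are PMD by the column heading. New FDG-positive lymphoma lesions also score 5 and are barred from PMR and SMD. PMD leads to overall PD, so this cell works.
- *CT/MRI cell.* Involvement shown by biopsy without new FDG-avid foci cannot produce anatomic PD, because the anatomic table has no marrow column. It cannot enter as a new lesion either, because the new-lesion text requires something visible at the timepoint. It has no route to PD.

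**3. When this can occur.**
- *Non-FDG-avid disease.* The Schedule of Activities requires no follow-up PET unless clinically indicated.
- *CT-only visits.* FDG-avid participants need PET at baseline, Weeks 12 and 24, to confirm CR, or if clinically indicated. At other visits CT may be the main determinant, so anatomic PR or SD stands. Anatomic CR is barred by the marrow rule, but no replacement category is named.
- *Carried-forward PET.* Carry-forward stops only for worsening on CT. A positive biopsy does not stop an earlier PMR from being reused.
- *A PET at the visit that shows no new foci while the biopsy is positive.* The biopsy settles marrow status, but no response category follows from it.

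**4. Size.** ORR = responders / n, with exact 95% Clopper-Pearson intervals as in Section 9.6.2. The responder counts are assumed for illustration; the denominators are the ends of the 6 to 12 enrolment range.
- n = 6: 2/6 = 33.3% (4.3 to 77.7) becomes 1/6 = 16.7% (0.4 to 64.1).
- n = 12: 3/12 = 25.0% (5.5 to 57.2) becomes 2/12 = 16.7% (2.1 to 48.4).

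Section 8.2.2 evaluates ORR by disease cohort. The Lugano denominator may be smaller, and the shift of 1/n correspondingly larger.

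**The case against.** The best defence has four parts.

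**The PET route works.** A reader might infer that all biopsy-proven marrow progression is graded PR or SD. The documents do not support that: PET-detected, biopsy-confirmed new foci are PMD and hence PD. This stands and limits the point to the CT/MRI cell.

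**Marrow is recognised elsewhere.** Section 8.2.2.1.2 names marrow examination among the non-imaging parameters on which progression can rest in some indications, and 10.9.2.5 says clinical data are combined with imaging. An investigator could therefore record PD on judgement. This shows that marrow matters, but it does not override a table that assigns PR or SD whatever the marrow shows.

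**The biopsy requirement is no contradiction.** A reader might also infer a conflict between the PMD definition, which needs no biopsy for new FDG-positive lesions, and the marrow cell, which does. These are better read as a general rule beside a site-specific one. Section 10.9.2.4 gives the reason: marrow uptake can be reactive. This stands, and that conflict is not claimed.

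**The stakes are small.** It is tempting to say that DOR or PFS is overstated by at least one 12-week interval. That does not follow, because Section 8.2.2 allows earlier imaging when clinically indicated and 8.2.2.1.2 provides for a repeat assessment at 4 to 6 weeks. A spurious first PR also needs tumour response, new marrow lymphoma and a marrow sample together. No hypothesis is tested, and DOR is summarised only if responder numbers permit. All this stands and keeps the priority low.

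**Conclusion.** The inconsistency holds in the narrow form. Biopsy-proven new or recurrent marrow lymphoma without PMD or anatomic PD is PD under the Section 10.9.2.2 summary. Under 10.9.2.5 it is PR with PMR, SD with SMD, and has no row with CMR. When there is no PET it follows a table that takes no account of marrow.

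The consequence is confined to Lugano-assessed participants. One participant's best response could change, and DOR or PFS would run on until the next assessment showing PD. The documents do not say how often a marrow sample would reveal this; it is probably uncommon. The DLT and AE endpoints are unaffected. This is a low-priority correction, worth making because the rule as written misclassifies a progression that the protocol itself defines.

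The conclusion assumes that the overall-response table is applied as printed and that the marrow finding is new or recurrent. Marrow disease persisting from baseline is a different case, for which the *Any* entry under PMR and SMD raises no objection.

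**What to change.** Reconcile the tables in 10.9.2.3.2 and 10.9.2.5 with the summary in 10.9.2.2 by carrying the marrow criterion into the overall-response table:

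1. Add a row giving PD for biopsy-proven new or recurrent marrow involvement, whatever the metabolic and anatomic categories.
2. In the PMR and SMD rows, change the marrow entry so that it excludes new or recurrent involvement.
3. Add a row for CMR with a positive marrow, stating the category when the involvement is not new or recurrent.
4. State that the marrow rule also applies at CT-only visits, and that a positive result of this kind stops an earlier PET from being carried forward.

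The new row would change the 9 affected combinations (3 now PR, 3 now SD, 3 now without a row) to PD and leave the other 7 as they are. The rule should apply only to marrow results already obtained under the protocol. The cost is a few table cells and one or two sentences in Appendix 9, with no extra sampling, imaging or visits.

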### **10.9.2.3 Anatomic Disease Assessment**

Anatomic assessment specifically refers to the size of focal lesions or organs, assessed using computed tomography or magnetic resonance imaging. As stated previously, for simplicity the term “CT” will be used to represent all anatomic imaging.

#### **10.9.2.3.1 Screening (Baseline) Assessment**

##### **Documentation of focal lesions**

All focal lesions caused by lymphoma are identified at baseline and classified as measurable or non-measurable. Up to 6 of the measurable lesions are selected to serve as “target” lesions,

which are then followed quantitatively throughout the study. All other focal lesions are documented as “non-target” lesions, and evaluated qualitatively thereafter.

### **Measurable and non-measurable lesions**

Malignant lymph nodes (nodal lesions) are considered measurable if they are consistent with lymphoma, clearly and reproducibly measurable in 2 dimensions on an axial slice, and measure  $>1.5$  cm in LDi when assessed by CT/MRI scan, irrespective of scanner type and slice thickness/interval. Extranodal lesions are considered measurable if they are consistent with lymphoma, clearly and reproducibly measurable in 2 dimensions on an axial slice, and are  $\geq 1.0$  cm in both LDi and SDi when assessed by CT/MRI scan, regardless of slice thickness. In lymphomas that are FDG-avid, a lesion must be PET positive (show FDG uptake greater than the surrounding tissue) to be measurable.

Lesions considered non-measurable include:

- Lymph nodes and nodal masses that are PET positive and considered consistent with lymphoma, but that do not meet the size and reproducibility requirements to be considered measurable, and lesions visible on PET but not CT
- PET-negative lesions which meet the size criteria for measurability, and are considered consistent with lymphoma, in lymphoma that shows FDG avidity in other lesions
- Uni-dimensionally measurable lesions (clearly measurable in only 1 dimension)
- Extranodal lesions which do not meet the requirements for measurability, but are considered to be clearly due to lymphoma
- Truly non-measurable/assessable sites of disease, including:
  - Effusions and ascites
  - Bone lesions
  - Brain lesions, CNS lesions, leptomeningeal disease
  - Mucosal lesions in the gastrointestinal tract
  - Pleural, peritoneal or bowel wall thickening

### **Target and Non-target Lesions**

Up to 6 target lesions will be selected from among the measurable lesions and documented as target nodal and target extranodal lesions. Target lesions should be selected based on their size (largest lesions preferred) and suitability for reproducible measurements. Measurements of the LDi and SDi should be made in the axial plane on the slice of the tumor with the

longest in-plane diameter. Calculate the product of PPD for each target lesion and the SPD for all target lesions.

Non-target lesions will be all focal (nodal and extranodal) lesions that are consistent with lymphoma, but not chosen as target lesions, whether they were measurable or not.

Once lesions are designated as target or non-target, those designations may not change during later assessments.

### **Spleen Assessment at Baseline**

Splenic involvement will be assessed quantitatively, as a separate category from the assessment of measurable or non-measurable focal lesions. The spleen length will be measured from cranial to caudal. All spleen measurements referred to hereafter will refer to this craniocaudal measurement. The spleen is considered normal if it is less than 13 cm, or if the spleen has been removed surgically. It is considered enlarged if it is greater than 13 cm in length. The portion of the measurement that exceeds 13 cm will be considered the abnormal portion.

### **Liver Assessment at Baseline**

Hepatic involvement will be assessed qualitatively, separately from the assessment of measurable or non-measurable disease. At baseline, the liver will be assessed qualitatively as either normal or enlarged, and should only be documented as enlarged if there is clear evidence (based on biopsy or imaging) that the enlargement is due to infiltration by lymphoma, and not to benign causes.

## **10.9.2.3.2 Post-baseline Assessment**

### **Target lesions**

At every timepoint after screening, each target lesion is measured. Calculate the PPD for each target lesion and the SPD for all target lesions together. Response categories are as defined below:

- Complete Response (CR): All target lymph nodes must have regressed to normal size defined as  $\leq 1.5$  cm in LDi. Target extranodal sites must be absent (0 by 0 cm).
- Partial Response (PR):  $\geq 50\%$  decrease in SPD of target lesions from baseline, and no individual lesion meets the criteria for progression.
- Progressive Disease (PD): Target lesion progression is based on the progression of any single lesion (not a change in the SPD), which meets all of the following requirements:
  - The lesion must have increased by  $\geq 50\%$  from its nadir in PPD.
  - For a lymph node, it must be  $> 1.5$  cm in LDi, and for an extranodal lesion it must be  $\geq 1.0$  cm in LDi.

- And one of the following:
  - o For lesions <2 cm at nadir, the lesion's LDi or SDi must have increased by  $\geq 0.5$  cm at the current timepoint from its nadir.
  - o For lesions  $\geq 2$  cm at nadir, the lesion's LDi or SDi must have increased by  $\geq 1$  cm at the current timepoint from its nadir.
- Stable Disease (SD): A target lesion assessment of SD requires all of the following:
  - Target lesions do not meet the criteria for CR or PR
  - No individual lesion meets the criteria for progression
- Not Evaluable (NE): When a target lesion identified at baseline cannot be evaluated at a post-baseline timepoint due to missing imaging, poor image quality, changes in the lesion or background that precludes assessment, or focal therapy or other procedures that change the lesion size, the target lesion assessment will be NE, unless progression is assessed in another target lesion.

### **Non-target lesions**

Non-target lesions will be assessed at each post-baseline timepoint individually and as a group. Response categories are as defined below:

- Absent/Normalized (CR): All individual non-target nodal lesions must have returned to normal size. All extranodal lesions must have disappeared.
- Unequivocal Progression (PD): Any individual non-target lesion must unequivocally progress in the context of the overall disease burden to be assessed as PD. For increased thickening of the wall of a hollow viscus, the reviewer will use their cautious judgment to determine whether the increase is most likely caused by disease progression.
  - PD should not be called based on enlarging pleural effusions or ascites, or enlarging lytic bone lesions, and rather, the overall assessment should be based on the rest of the disease burden.
- Stable Disease (SD): At least 1 non-target lesion is still present, or a node enlarged, without any individual lesions showing unequivocal progression.
- Not Evaluable (NE): When an individual non-target lesion lymph node, extranodal lesion, or non-measurable disease cannot be assessed at a post-baseline timepoint due to missing imaging, poor image quality, changes in the lesion or background that precludes assessment, or focal therapy to a lesion, the individual non-target lesion will be assessed as NE. The assessment of the non-target lesions as a whole will be NE if any of the non-target lesions are NE and none are PD.

